**H2.3:** The overall effects of MET treatment on SGA adherence will be mediated by degree of weight abrogation, and this relationship will be stronger among girls than boys. We anticipate a possibly complex relationship between abrogation of weight gain (associated with MET) and SGA adherence, because weight gain may also be avoided via SGA non-adherence (at the probable cost of sub-optimal psychiatric outcomes; see Specific Aim 3). A statistical framework (marginal structural models) to accommodate this possibility is described in the Statistical Analysis Plan.

**Specific Aim 3:** Assess the overall and subgroup-specific impact of MET+LIFE vs. LIFE alone on **psychiatric symptom burden, psychotropic treatment changes, and overall and weight-related QoL**, including assessment of how these effects are mediated by MET effects on weight gain and SGA adherence.

**H3.1:** Overall, assignment to treatment with MET will be associated with lower psychiatric symptom burden, decreased risk for symptom-driven treatment changes, and greater improvements in overall and weight-related QoL than LIFE alone at both 6 and 24 months, post-randomization.

**H3.2:** (HTE): MET effects on psychiatric symptoms will be smaller in patients who meet full DSM criteria for a BSD.

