**Figure 1: MET prevention and intervention effects SGA-induced weight gain in youth**  
**Group1=SGA-non-naïve Group 2= SGA-naïve**

This group difference resulted in part from the immediate decrease in BMI z score in the SGA naïve group (BMI z score decreased by 0.23). BMI z score of the SGA non- naïve group decreased by 0.27+0.5 during the 6 months on MET. SGA naïve patients responded at lower MET doses than SGA non-naïve patients ( $764 \pm 225$  mg/d vs.  $834 \pm 285$ ). Additional determinates of MET response were: 1) Higher baseline BMI z score ( $p<0.0001$ ); 2) Longer length of SGA treatment prior to MET initiation ( $p=0.049$ ); and, 3) A  $> 7\%$  increase in weight over the 2 months prior to starting MET ( $p=0.0007$ ). These data confirm our previous results that MET abrogates SGA-induced abnormal weight gain in youth and also adds concerning information that a larger proportion of youth on SGAs are affected by weight gain than previously reported.

**IMPACT Study:** Most recently, [name] completed a large rigorously controlled NIMH-supported study of youth with psychiatric disorders and  $\text{BMI} > 85\%$ ile and SGA-related weight gain. Participants were randomized to 1 of 3 arms: 1) continuation of current SGA (control arm) ( $N=44$ ); 2) switch from current SGA to lower-risk agent (LRA) ( $N=30$ ) or 3) co-treatment with MET + continuation of current SGA (MET) ( $N=46$ ).

Sample characteristics were as follows: Age: 13.7 (7.6-19.9;  $<18=88\%$ ) Male=65% Hispanic:12% Black: 28%. At 12 and 24 weeks there was a significant decrease in BMI Z-scores in the MET (-0.034, -0.088, respectively) and LRA (-0.051, -0.112) groups compared with the control group (+0.026, +0.040). Additionally, at 24 months weight gain in the control group was 8.5lbs and 0.3lbs in the LRA group. In contrast, the MET group had an average decrease of -0.4lbs. 14.9% in the MET lost  $>5\%$  of weight compared to 2.3% in the control group and 10.0% in the LRA group (Fisher's exact,  $p=0.059$ ). Importantly, dropout rates in the LRA (39%) and control (28%) groups were higher than in the MET (24%) group. The most common (58%) reason for discontinuation in the LRA group was "inadequate therapeutic effect."

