### **STUDY SCHEDULE AND TREATMENT**

Since MOBILITY is a pragmatic study, we will collect the above information, when possible, and in conjunction with patients' clinical visits. We will allow for data collection approximately monthly for the first three months, followed by every three months thereafter, for a total duration of 24 months. However, these visits and timeline are just guidelines. Data will be collected through information acquired during clinical visits. There is no minimum number of visits required for patients to continue to participate in MOBILITY and have their data collected. However, sites should not schedule patient appointments exclusively to conduct study specific visits or procedures. Therefore, it is anticipated that **not all study visits or procedures will be completed for every patient. However, we will emphasize the importance of collecting Month 6 and 24 data since those are primary outcomes.** Labs tests that are recommended in the Schedule of Events are based upon standard clinical practice guidelines, but will not be required for continuation in the study.

Each site will have a copy of the MOBILITY Projected Visit Dates Spreadsheet (also found on the website: MOBILITYstudy.org). The site coordinator will enter the patient's baseline visit date where indicated, and the recommended visit schedules will auto-populate. However, once patients are randomized at baseline, MOBILITY is primarily an observational pragmatic study, therefore, data will be collected only at clinical appointments.

**Screening/Baseline Procedures:** At screening and following informed consent/assent and review of initial study criteria, we will obtain demographic and clinical information as follows:

Demographic and Clinical Characteristics: Site staff will record patients' date of birth, sex, type of insurance, contact information, and prior type and duration of psychiatric treatments. Patients will report current daily nicotine intake (packs/day) and whether they currently use other drugs (checking all that apply from a list of common drugs). Data on treatments and substance use will also be collected at six-

month intervals.

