for data entry and real time validation (e.g., automated data type and range checks); 2) HIPAA-compliant and 21 CFR Part 11-ready audit trails for tracking data manipulation and exports; 3) record locking and electronic signature functions; 4) control of view/edit rights; 5) a tool for reporting, monitoring and querying patient records; and 6) automated export to common statistical packages. REDCap is hosted on a network specially designed to support the rigorous security and compliance requirements of clinical research projects. Administered by the CCHMC Division of Biomedical Informatics, this network features multiple firewalls and a central facility for managing hosted systems and users, creating another layer of access control and audit capability on top of what REDCap already provides (e.g., user access can be monitored and controlled at the network level without making any changes within REDCap itself). These capabilities are available to authorized network administrators and REDCap study owners only, and user access changes are documented by an audit trail. The data management team will monitor the database throughout the study to assure that data are complete and accurate.

**Analyses of Specific Aims:** Each specific aim involves assessment of domains that are hypothesized to be affected by MET either directly or indirectly through other domains. Our approach to potential HTE distinguishes effect moderators from mediators of distal outcomes. Moderators include fixed patient characteristics and pre-treatment covariates values. Mediators include variables that are hypothesized to be affected by MET treatment and that may in turn affect other outcomes. We will utilize generalized linear mixed models (GLMM), which allow for outcomes from a range of distributions and will include random effects to account for unspecified causes of variation among sites and patients, and subgroup-specific coefficients to assess HTE.

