The basic model for outcomes will be a GLMM with change from baseline to either 6- or 24- months as the dependent variable. Independent variables will include fixed-effect terms for randomized treatment group (MET), baseline value of the outcome, and random site effects. For HTE analyses, a baseline value-by-MET interaction (to assess HTE due to baseline status) will be included, and for particular domains additional continuous or categorical covariates and treatment-by-covariate interaction terms will be added to assess HTE. Outcomes within each domain will share the same set of HTE terms, specified in the Specific Aims. Because the subgroups are in general correlated (e.g., duration of SGA treatment, weight gain history and psychotropic weight burden will be correlated with baseline BMI), we will include multiple first-order HTE terms simultaneously (to assess heterogeneity independently attributable to each moderator), but will also fit separate models for each term to gauge the impact of this correlation on our conclusions. Higher-order treatment-by-covariate interactions will not be included a priori, but will be explored with rigorous adjustment for multiple testing, using step-down testing (removing highest-order interaction terms first) or information criteria based on penalized likelihoods to guide model selection.

**Marginal Structural Modeling for Causal Inference:** SA1 concerns the overall and sub-group specific effects of MET on abrogation of weight gain (with changes in BMI z-score from baseline as outcomes) and metabolic health, particularly metabolic syndrome and its component criteria. BMI and adherence measures are obtained at all study visits, so our models for these measures will use all available observations by treating the longitudinal series of changes in these variables and SGA treatment as dynamically dependent on each other. We will use marginal structural models to address this bi-directional dependence, computing the probability of SGA treatment regimen change at each visit within weight gain treatment regimen groups and using appropriately normalized versions of the inverse of the probability as the stabilized weights.

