Exacerbation of BSD is also a risk, however patients will be treated for BSD as clinical indicated and there are no restrictions on psychotropic medications use. Patients will be monitored closely by site clinicians who will use the YMRS to systematically assess manic symptoms and the PHQ-9 item #9, to assess current suicidality. Patients will remain in the study even if they require a change in treatment or psychiatric hospitalization. These events will be recorded as psychiatric symptom burden outcomes. Patients who become pregnant during their study participation will continue to be followed. We will encourage treating clinicians to discontinue metformin if it is being prescribed for study participation and to consult with the prescribing clinician prior to discontinuation, if it is prescribed by another clinician and for reasons unrelated to the study.

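### H3.1 treats symptom-driven treatment changes as a risk at 6 and 24 months, but the only stated outcome model is change from baseline, with no event definition and no account of how long each patient was observed

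*Combined protocol and SAP*

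**What the plan says.** In A. Specific Aims, H3.1 includes "decreased risk for symptom-driven treatment changes" among the benefits expected over "LIFE alone at both 6 and 24 months, post-randomization". Section G.a (Level of Risk Description) keeps patients in the study after a change of treatment or a psychiatric hospitalisation and adds: "These events will be recorded as psychiatric symptom burden outcomes".

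Section E.b (Data Analysis and Data Monitoring) gives one general model: "The basic model for outcomes will be a GLMM with change from baseline to either 6- or 24- months as the dependent variable". The same section says of the model family: "We will utilize generalized linear mixed models (GLMM), which allow for outcomes from a range of distributions". It names no distribution, link or offset for event outcomes. Repeated observations are promised for two measures only: "BMI and adherence measures are obtained at all study visits, so our models for these measures will use all available observations". Change of SGA regimen enters the marginal structural model as a source of weights, not as an outcome. Multiple imputation is described only for electronically monitored adherence.

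On completeness of observation, Study Schedule and Treatment says: "There is no minimum number of visits required for patients to continue to participate in MOBILITY and have their data collected". It also expects some visits to be missed. Section F.f (Recruitment Plans) expects retention of about 90% over two years, not split by arm. Section E.f (Estimated Period of Time) has 75% of patients recruited by month 45 and the last at month 57. Section E.b completes the long-term analysis by month 69.

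**The concern.** A treatment change or a hospitalisation has no baseline value to change from, and its probability grows with the time a patient is watched. To count a patient as event-free at month 24, someone must have observed that patient to month 24. The plan defines neither the event nor the scoring of a patient last seen at, say, month 9 or month 18, and its stated model has no term for observed time.

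Two competent analysts could therefore report different 24-month risks and different treatment effects for the same named hypothesis. In an open-label trial, that choice could be made after the data had been seen. H3.1 is where the trial asks whether metformin reduces psychiatric destabilisation, so the choice should be fixed in advance.

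**Working it through.** The plan gives no event rate, power or event count for this outcome, so there is no figure of its own to reproduce.

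**1. Calendar.** Inputs are last entry at month 57, 75% recruited by month 45 (E.f) and long-term analysis by month 69 (E.b).
- Month 6: 57 + 6 = 63, which is before 69. Everyone can reach it.
- Month 24: 57 + 24 = 81, which is after 69 and after the 72-month study period. E.b nevertheless describes 24-month follow-up as complete by month 69.
- A patient can reach month 24 by month 69 only if recruited by 69 − 24 = month 45. The stated milestone puts 75% there, so 25% cannot: 0.25 × 1800 = 450, or 225 per arm. If they enter evenly between months 45 and 57, their follow-up runs from 24 down to 12 months, mean 18.

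**2. Scoring no record as no event.** Assumptions: constant event hazard *l*, independent constant dropout hazard *d*, and a true 24-month risk of 40% (the documents give none). Dropout is 10% (F.f).
- *l* = −ln(0.60)/24 = 0.02128; *d* = −ln(0.90)/24 = 0.00439; sum *s* = 0.02567.
- Full 24 months available: (*l*/*s*)(1 − e^(−24*s*)) = 0.829 × 0.460 = **38.1%**.
- Late entrants (12 to 24 months): (*l*/*s*)[1 − (e^(−12*s*) − e^(−24*s*))/(12*s*)] = 0.829 × 0.3676 = 30.5%.
- Combined: 0.75 × 38.1% + 0.25 × 30.5% = **36.2%**.

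| True 24-month risk (assumed) | Read with 10% dropout | With month-69 cut added |
|---|---|---|
| 20% | 19.0% | 18.0% |
| 35% | 33.3% | 31.6% |
| 40% | 38.1% | 36.2% |
| 50% | 47.7% | 45.5% |

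With equal 10% dropout, a true 34% against 40% (6 points) reads as a 5.7-point difference, and as 5.5 points with the cut.

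**3. Scoring only patients seen at month 24.** Same assumptions, 40% risk, per arm of 900.
- Events recorded in the 225 late entrants: 225 × 0.305 = 69.
- Among the other 675, those with an event who then leave: (1 − e^(−24*d*)) − (*d*/*s*)(1 − e^(−24*s*)) = 0.100 − 0.171 × 0.460 = 0.0213; 675 × 0.0213 = 14.
- Discarded: 69 + 14 = 83 of 900 × 0.362 = 326 recorded events, about 25%.

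**4. Difference between arms.** With equal follow-up and equal true risk, the false difference is 0. The only dropout figures by arm come from the earlier three-arm randomised study under C. Preliminary Studies: "dropout rates in the LRA (39%) and control (28%) groups were higher than in the MET (24%) group". Taken as 24-month rates without the calendar cut, 24% and 28% turn a true 40% in both arms into 35.4% (MET) and 34.6% (LIFE). The gap is 0.8 points against a standard error of 2.25 points, or 0.36 SE. Exchanging the two rates reverses the sign.

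**The case against.** The strongest reply is that the general model is called basic and belongs to a family that admits binary and count outcomes. A visit-level binary model, or a count model with an offset, would fit within it. On that reading the plan is silent on this outcome and does not prescribe a faulty scoring. That is fair, and fixed-time scoring is not forced on the analyst. Silence on the event definition, the distribution and the handling of observed time still leaves the analysis of a named hypothesis open.

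A reader might infer that the risk will be understated unequally by arm, to metformin's disadvantage. The documents do not support that.
- It requires leavers to be scored as event-free, which is nowhere stated.
- It requires unequal follow-up, which is nowhere given for this trial. The 28% and 24% come from 44 control and 46 metformin patients in a different design. The 4-point difference has an approximate 95% interval of −14 to +22 points (0.04 ± 1.96 × 0.092).
- Calendar truncation should be balanced by 1:1 randomisation.
- Follow-up continues after a treatment change or hospitalisation.

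Scoring only completers is also not biased when dropout is independent of the event; it then loses precision. Bias there needs informative dropout, and its direction could be either way.

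Finally, this is one component of H3.1, and the primary outcome is BMI z-score. H3.1 also says at, not by, 6 and 24 months, so reading it as cumulative risk is an interpretation, though the natural one for a risk of events.

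**Conclusion.** The point holds as a gap in specification with a modest, conditional effect. The stated model does not suit these outcomes, and no section available for review defines the event or says how incomplete observation is handled.

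At month 24 this affects a quarter of patients through the calendar alone, in addition to about 10% loss. An assumed 40% risk would read as about 36% if absence of a record is scored as absence of an event. About a quarter of recorded events would be set aside if only patients seen at month 24 count. Month 6 is exposed to dropout and missed visits but not to the calendar.

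No directional bias between arms is claimed. The sizes rest on assumed event risks, constant and independent hazards, accrual on the stated milestones (even after month 45) and analysis at month 69. If analysis waited until month 81 the calendar part would disappear and the dropout part would remain. The change is worth making because it is cheap; the trial's main result does not depend on it.

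**What to change.** In the analysis section:
- Define a symptom-driven treatment change (which changes count, and from when), and record the reason for each change.
- Analyse treatment change and psychiatric hospitalisation as time to first event by randomised arm, placing a change in the interval between the visits that bracket it. If repeated events matter, use a count model with log observed time as offset.
- Censor at the last visit with a recorded medication list, and state that no patient is scored event-free beyond it. For hospitalisation, use the last visit at which it was ascertained.
- Report the 6- and 24-month risks from that curve, and follow-up time by arm.
- Add a sensitivity analysis for informative dropout.
- Reconcile the month-69 analysis date with last entry at month 57.

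The cost is plan wording and modest extra programming. The medication list is already scheduled at every visit in Table 2, but nothing says that it captures the reason for a change, so that field must be confirmed or added. Table 2 has no separate row for hospitalisation, so the source of its date needs the same check. The main analysis would assume that censoring is non-informative given arm and covariates, which is why the sensitivity analysis is needed.

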## B. BACKGROUND AND SIGNIFICANCE

**Overweight and Obese Youth with Bipolar Spectrum Disorders (BSD):** 1 out of 3 youth in the United States is overweight or obese. The rising prevalence of obesity and associated metabolic problems has led to elevated healthcare costs, marked morbidity, and high mortality. Compared with the general population, individuals with BSD have higher rates of obesity, poor access to medical care and premature mortality, largely due to the greater incidence of cardiovascular disease. BSD are common psychiatric illnesses characterized by periods of mania, hypomania, and depression. Epidemiological studies suggest that BSD most commonly begin during adolescence and have a prevalence rate of up to 5% in youth. Youth with BSD have a relapsing and remitting illness course, with greater functional impairment, poorer quality of life (QoL), and greater economic burden than those with later-onset BSD as well as youth with chronic medical and behavioral illnesses (e.g., asthma, heart conditions, and depression). A major factor contributing to poor outcomes is the high rate of overweight or obesity in youth with BSD. Rates of overweight/obesity in youth with BSD vary in studies between 45-80%, more than double that of the general population. Overweight or obese youth with BSD have a more severe illness course, with a greater number of hospitalizations and higher rates of substance use disorders and physical abuse than youth with BSD who are not overweight or obese. Moreover, these youth typically become overweight or obese adults with more medical problems and higher rates of psychiatric symptom recurrence, hospitalizations, and suicidality as well as elevated morbidity and mortality. Therefore, prevention and intervention for weight gain in youth with BSD is of significant public health interest and clinical concern.

### **Treatment with Second Generation Antipsychotics (SGAs) is on the Rise for Youth with BSD:**

Maximizing mood stability and minimizing medication side effects are the primary treatment goals for improving overall outcome and QoL of youth with BSD. Over the past decade, there has been an increase in evidence-based treatments for youth with BSD. There have been at least 10 double-blind randomized controlled trials demonstrating that SGAs are effective for treating mania and depression in youth with bipolar disorder. These studies have led to the United States Food and Drug Administration's (USFDA) approval of four SGAs (olanzapine, risperidone, aripiprazole, and quetiapine) for the treatment of mania in youth and of olanzapine/fluoxetine combination as the only evidence-based treatment for depression associated with bipolar disorder in youth. Furthermore, in contrast to adults with bipolar disorder, several studies have recently demonstrated that youth with BSD have a significantly greater response to SGAs than to other mood stabilizing medications (e.g., lithium, valproic acid). In fact, in the only double-blind placebo-controlled study of lithium for mania in youth, only 38% had a > 50% reduction in symptoms of mania, as compared to most studies of SGAs, which report response rates of 55-80%. Without equally efficacious evidence-based options for treating BSD in youth, SGAs use will likely continue to increase. Although treatment with SGAs offers advantages over conventional antipsychotics (e.g., haloperidol), such as lower rates of extrapyramidal syndromes, there is significant concern about the dramatic increase in SGA prescriptions for youth, because younger patients are more susceptible to SGA-related side effects than adults and discontinuing SGAs without an effective alternative medication is not a treatment option for many youth with BSD.

**Treatment with SGAs often leads to considerable symptom improvement, but is very commonly associated with substantial weight gain early in treatment.** A primary etiology of overweight/obesity in youth with BSD is SGA exposure. SGA-induced weight gain increases their already elevated long-term risk of cardiovascular disease and premature mortality. Furthermore, metabolic syndrome is a common, more immediate consequence of SGA treatment in youth. The risk for SGA-induced weight gain is much greater in youth than in adults. The weight gain associated with SGAs is often dramatic and places these youth at risk for dyslipidemias and insulin resistance, which may progress to diabetes. Weight gain typically begins immediately following SGA initiation. In a recent study, over 50% of 272 treatment-naïve youth gained >7% of their baseline weight within 12 weeks. These data may underestimate the problem; recently, we determined that 80% of SGA-treated youth gained > 7% of their baseline weight over two months while hospitalized at our Academic Health Center. The so-called “appetite aggression” induced by SGAs may lead to violent behaviors and medication refusal following food restraint.

Although all SGAs cause some weight gain in youth, the amount of weight gain varies by specific SGA, prior exposure to SGAs, and the individual. Treatment-naïve youth may be more susceptible to SGA-related weight gain. Nonetheless, weight gain typically continues over the course of treatment. Indeed, we found 1 lb/week weight gain over 16 weeks in youth prescribed olanzapine, risperidone, or quetiapine for up to one year. While it is unclear whether SGA-related weight gain is dose-dependent, SGA polypharmacy may be associated with greater risk of metabolic syndrome compared to SGA monotherapy.

SGA-related weight gain in this already overweight/obese population is particularly problematic, as most obese youth become obese adults. In fact, studies report that approximately 70% of youth treated with SGAs are overweight or obese. Although relatively few youth develop diabetes because of their large insulin reserves, 12-50% of youth treated with SGAs experience hyperinsulinemia and dyslipidemia, which are related to the development of metabolic syndrome and cardiovascular morbidity and mortality. Additionally, obesity during youth influences later morbidity and mortality to a greater extent than obesity present only during adult life and the relationship of overweight, obesity, and metabolic abnormalities to poor cardiovascular outcomes is accelerated when age-inappropriate weight gain and metabolic abnormalities begin during development. The immediate and dramatic nature of the anthropometric and metabolic effects is a common reason for SGA discontinuation, is predictive of medication non-adherence in youth, and has a negative impact on overall satisfaction with care and illness outcome. Moreover, poor adherence in youth with BSD increases the likelihood of relapse and is associated with substance use.

**Evidence-Based and Accessible Strategies for Managing SGA-related Weight Gain and Obesity in Youth with BSD are Urgently Needed.** The mechanisms of SGA-related weight gain are likely multi-factorial, involving effects on central and peripheral hormonal, neuronal, and metabolic regulation of energy intake and consumption. Regardless, the widespread and devastating impact of SGA-related weight gain on psychiatric symptoms, other health outcomes, and health care costs have led to an immediate need for standardized, evidence-based approaches to manage this common and serious side effect.

Despite SGA-related medical concerns, these medications are highly effective for treating BSD and thus, given a choice, patients and their families would prefer to effectively manage this side effect rather than change medications and risk relapse (see Significance). Nonetheless, discontinuation of SGAs or switching to a lower-risk SGA is a potential strategy to manage weight gain. Unfortunately, switching SGAs produces limited or inconsistent improvements in weight and metabolic outcomes, along with some psychiatric risk. Indeed, in the recently completed IMPACT study, youth treated with SGAs who were randomized to switching to an SGA with lower weight burden experienced significantly greater rates of psychiatric symptom exacerbation than those maintained on their original SGA with lifestyle intervention or metformin added.

**Healthy Lifestyle Interventions** promote physical activity and dietary lifestyle changes. Healthy lifestyle programs designed for youth, such as the “Healthy Eating Plan” associated with Healthworks!, developed and tested by [name] (Co-Investigator), may lead to weight loss in obese youth. However, some studies show only limited benefits and involve programs that are not easily accessible. Studies of older adolescents and adults treated with SGAs found that healthy lifestyle interventions are effective for preventing weight gain and for weight loss, respectively, as well as for improving QoL, particularly when used early in the course of SGA treatment. In general, 2-5% reduction in weight or 1-1.5 body mass index (BMI) units is reported in studies of healthy lifestyle interventions for patients with mental health disorders. However, these studies suffer from high dropout rates, small sample sizes, and short duration.

Furthermore, the effects on weight and other metabolic parameters are small compared with pharmacological interventions. Despite these limitations, The American Medical Association (AMA) 2007 provides guidelines on interventions for youth ages 2-19 years old who meet CDC criteria for “at risk for overweight” and “overweight” (BMI%  $\geq$ 85%ile) that involve simple education regarding diet and physical activity, i.e., healthy lifestyle intervention. Although these guidelines were not specifically developed for mentally ill youth, the approach has advantages for this population, including simple dietary guidelines and inexpensive strategies to reduce sedentary behavior. This approach is similar to the standardized Healthy Eating Plan and Physical Activity education (LIFE) that will be provided to each participant of the proposed trial.

**Metformin (MET) for Obesity in Youth.** Pharmacological therapies, such as MET, supplement the effects of lifestyle interventions for weight loss. MET targets a molecular mechanism for weight gain, i.e., hypothalamic neuronal AMP kinase, a metabolic “fuel sensor”. SGAs directly affect hypothalamic AMP kinase through histamine H1 receptors, decreasing leptin and insulin sensitivity. MET is an oral anti-hyperglycemic, insulin- sensitizing agent that reduces hepatic gluconeogenesis and is noteworthy among diabetes treatments for not promoting weight gain. MET is approved by the USFDA for treatment of type II diabetes in youth >10 years. MET decreases food intake in obese, non-diabetic individuals. A recent meta-analysis of 14 randomized clinical trials (N>1000) examining the effectiveness of MET for obesity in youth found an average BMI reduction of -1.38 (95% CI, -1.93 to -0.82) over 6 months compared with controls. Although a greater effect was seen for youth with a BMI > 35 at baseline, the authors concluded that a large trial is needed to determine the benefits to subgroups. Smaller meta-analyses report BMI reductions of -1.1 to -2.7 in obese youth compared with placebo or lifestyle intervention alone, in trials ranging from 6-12 months with MET dosages of 1000-2000mg/day. Fasting insulin resistance, glucose homeostasis, and dyslipidemia improved after MET. In these studies of youth from 8-18 years old, MET was well-tolerated at up to 2000mg/day.

MET is extremely safe in youth. Lactic acidosis is extremely rare, especially in the non-elderly and those with creatinine levels < 1.4, and the risk of neuropathy from chronic vitamin deficiency is low. MET for Weight Gain in Patients Treated with SGAs. We chose MET over other evidence-based medications for weight loss (e.g., orlistat, sibutramine, or topiramate) because MET is the only medication that has been systematically studied for reducing weight in adults and youth treated with SGAs and because of its superior tolerability and safety profile when prescribed in conjunction with SGAs. Indeed, we first reported that MET is safe and effective for minimizing weight gain in youth taking SGAs. Furthermore, in our randomized, placebo-controlled study, MET was associated with weight loss and improved insulin sensitivity, minimal discontinuation and no significant side effects other than transient gastrointestinal symptoms. In contrast, 1 in 6 patients discontinued orlistat and 1 in 2 patients discontinued sibutramine because of side effects. Additionally, although topiramate is effective for weight loss, cognitive “slowing” commonly leads to discontinuation. Subsequent to our studies, the utility of MET for weight loss in patients treated with SGAs has been confirmed in several RCTs and meta-analyses. In fact, there are now seven meta-analyses of treatments for weight gain and/or cardiovascular risk factors in patients taking SGAs.

Most recently, Gierisch et al, conducted a meta-analysis of studies of patients taking SGAs who were treated for weight gain and reported that adding MET was the only intervention studied to date that improves metabolic parameters, although, “comparative effectiveness studies are needed to test multi-modal strategies.” In another review of 11 MET studies (N=685) lasting on average 15.5 weeks, we determined that MET: 1) Produces statistically and clinically significant weight loss (-3.1 kg; 95% CI -4.5 to -1.6); 2) Improves lipid and glucose levels; 3) Is well tolerated; and 4) That weight gain resumes after stopping MET. We also concluded that MET’s effects might continue beyond 16 weeks, but noted there is a paucity of long-term studies. Although MET may be even more effective for prevention (i.e.,

[figure not shown]
when MET is started concurrently with an SGA) rather than intervention (i.e., participants were started on MET when on a stable dose of SGA), there have been only 2 prevention studies. While these studies were both from China and are therefore difficult to compare to studies conducted in the U.S., their findings are highly consistent with our preliminary data. Therefore, based on our patient surveys and these data, we opted to include both treatment-naïve and non-naïve patients in our proposed pragmatic trial. This would be the first study to directly examine differences in MET's effectiveness for prevention vs. intervention for weight gain in youth taking SGAs. Only one trial has compared MET alone, placebo plus healthy lifestyle intervention, and MET plus healthy lifestyle intervention: Wu et al. reported significant weight reduction and improved glucose and insulin levels for combined MET plus healthy lifestyle intervention compared with either alone. Based on these studies, the following recommendations were made: 1) The duration of future MET studies must be longer than 16 weeks to provide long-term efficacy data; 2) Larger studies are necessary to identify mediators and moderators; 3) Studies of MET in comparison to or combined with other strategies is much needed; 4) Because not all patients respond to MET, it is necessary to study heterogeneity of treatment effects (i.e., who is the best candidate for MET).

In summary, meta-analyses confirm that treatment with MET is the strategy for which there is the most evidence for weight loss in patients taking SGAs. However, each of the meta-analyses conclude that large- scale studies of MET in community settings and for long duration are urgently needed. We propose to conduct a pragmatic trial that addresses each of these gaps in evidence by investigating the long-term effectiveness of MET in obese and overweight youth with BSD, treated with SGAs in a community setting.

